There have been limited studies aimed at the treatment of myofascial pain syndrome in the acute setting of a TKA. Mayoral et al. (2013) conducted a randomized double-blinded, placebo-controlled clinical trial where patients who underwent a TKA had dry needling completed in the pre-operative and intra-operative setting. This study demonstrated an improvement in pain scores within the first month of surgery in the dry needling group compared to a sham group. This has been the only study to date to address direct intervention for myofascial pain syndrome around the operative time frame. Henry et al. (2012) conducted a prospective study in which patients on the waitlist for a TKA were treated with trigger point injections; patients reported an improvement in pain up until the TKA procedure could be completed. Although Henry et al. did not assess pain in the post-operative setting, this study nonetheless demonstrated that myofascial pain syndrome is a component of osteoarthritis.

Despite these favorable results there are no studies that look at trigger point injections in the post-surgical setting. The aim of this study is to perform trigger point injections with administration of a local anesthetic immediately following TKA to assess the effect on pain scores. The trigger point injection/experimental group will be compared to a sham injections/control group where a superficial injection will be made into the dermis and no anesthetic will be injected. Injections will include two injections to four muscle bellies: the vastus medialis, vastus lateralis, medial, and lateral gastrocnemius muscle belly. Injections will include 0.5 mL of lidocaine without epinephrine and will be outside of the operative area distal and proximal to the joint, the popliteal fossa and incision site. With each injection the plunger will be pulled back to ensure placement of the needle is outside vascular structures. To assess the primary outcome measures, patients will complete a Visual Analogue Scale (VAS) which ranges from 0 (no pain) to 100 (severe intolerable pain) on post operative day (POD) 1 and at follow-up visits during weeks 2 and 6. The secondary outcome will assess how much opioid medication (ie, MME) was used in the immediate post-operative period through the week 6 follow-up visit.

9.3

Objectives/Specific Aims/Research Questions:

Describe the purpose and objective(s) of the study, specific aims, and/or research questions /hypotheses

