those in the sham injection group an S. The study participants will not know which study group they will be assigned to. An equal number of participants will be included in each group (ie, trigger point injection vs. sham injection).

Step 3a: (Trigger point injection group) The principal investigator will identify relevant structures to include the vastus medialis, vastus lateralis, medial, and lateral gastrocnemius muscle bellies by utilizing anatomical landmarks. Once those structures are identified, each area will be prepped in an aseptic fashion with alcohol swabs. Two injections will be made in each muscle belly. Each injection will include 0.5 mL of 1% lidocaine without epinephrine. A total of eight injections will be administered with a total of 4 mLs of 1% lidocaine without epinephrine using a 1 ½" 25-gauge needle. A separate needle and syringe will be utilized for each of the four muscle bellies. Careful consideration to avoid neurovascular structures will be taken by retracting the plunger to ensure needle placement is outside vascular structures with each injection. A blind will be placed between the patient and the needle in order for the patient not to witness the injection, which is the same protocol as the sham injection. The blind used will be a drape or other soft item held by a person not involved with the study to obscure the vision of the subject during the injection and allow the investigator to use both hands to safely conduct the injection and aspiration procedure. The local anesthetic will be massaged into the area to ensure the medication disperses thoroughly into the muscle belly. After the needle is removed, the area will be cleaned with alcohol swabs and a bandage will be applied. This will be completed on POD 0 (ie, the day of the TKA procedure). Within the informed consent the consenting verbiage will ensure that the participants will not be able to identify injection technique that will identify whether they are in the sham or experimental group.

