Step 3b: (Sham injection group) The principal investigator will identify relevant structures to include the vastus medialis, vastus lateralis, medial and lateral gastrocnemius muscle. Once those structures are identified using anatomical landmarks, each area will be prepped in an aseptic fashion with alcohol swabs. A needle with a syringe filled with sterile water will be inserted into the epidermis to mimic an actual trigger point injection. The needle will be left in place for 3-5 seconds to create the false perception of injection anesthetic into the muscle groups. No sterile water will be injected into the participant. Since the effects from the anesthetic block will still be active and the injections will be administered in a position that prevents the participant from viewing the procedure, participants will not know that there is nothing being injected into the area. This will occur by placing a blind between the patient and the needle in order for the participant not to see that no water will be injected. The blind used will be a drape or other soft item held by a person not involved with the study to obscure the vision of the subject during the sham injection and allow the investigator to use both hands to safely conduct the sham injection procedure. After the needle is removed the area will be cleaned with alcohol swabs and a bandage will be applied. Four separate needles and syringes will be utilized for each location. This will be completed on POD 0 (ie the day of the TKA procedure). Within the informed consent the consenting verbiage will ensure that the participants will not be able to identify injection technique that will identify whether they are in the sham or experimental group.

Step 4: On POD0 (after TKA surgery, the investigator will review MHS Genesis to obtain demographic information (age, sex, beneficiary status, BMI), morphine milligrams equivalents (MME) using the Medication Administration Record (MAR) Summary, prior pain medication history, diabetic history, tobacco use, anesthetic block type, surgical site, ICD codes, complications, and discharge disposition.

Step 5: On POD1, participants in each study group will be provided with the VAS and Opioid Use questionnaires. The VAS pain scale questionnaire will be used to report average pain scores by placing a hash mark (/) on the numbered scale

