on the region that best represents their pain and writing the number (a whole number) on the form; scores range from 0 (no pain) to 100 (severe intolerable pain). The Opioid Use questionnaire will be used to document average opioid use following discharge. Both questionnaires will be completed by all participants at POD1, week 2 and week 6 visits. The VAS will be given to the participant with the intake form that is provided by the orthopedic technician, and the investigator will provide the Opioid Use questionnaire to the participant during the visit, and review the MAR Summary to obtain and calculate the total MME from POD0 to POD1 using MDCalc . Prior to ending the visit, the investigator will ask participants to bring in their opioids to be physically counted at their week 2 and week 6 visits.

Step 6: The investigator will provide a reminder phone call 1-2 days prior to the week 2 and week 6 appointments to ensure participants remember to bring in their medication.

Step 7: Participants return for the week 2 and week 6 visits. They are given VAS and Opioid Use questionnaires to complete, and opioid medication is counted. Once opioids have been accounted for, MME will be calculated.

10.2 Data Collection:

Describe all the data variables, information to be collected, the source of the data, and how the data will be operationally measured.

Injection type: Dichotomous variable. Trigger point or sham injection.

Visual analogue scale: Discrete variable. Will be scaled from 0 (no pain) to 100 (severe intolerable pain) and will be measured at POD1, week 2, and week 6. The VAS will be presented to the participant on paper.

Morphine milligram equivalent (MME): Discrete variable. Will be measured from POD 0 to POD1, then a total MME will be calculated from POD1 to week 2 and week 2 to week 6. This will be calculated utilizing the MME calculator on MDCalc.

Block: Categorical variable. Spinal, adductor or femoral nerve block determined by anesthesiology.

Age: Continuous variable. Age stated in years at time of surgery as stated in EHR.

Prior Pain Medications: Categorical variable. Obtained from EHR.

Discharge disposition: Dichotomous variable. Discharge to skilled nursing facility or home, discharge disposition will be reviewed in the discharge summary.

Active Duty, Dependent, Retiree: Categorical Variable.

Sex: Categorical (male, female). Obtained from EHR.

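### Participant blinding of the self-reported primary VAS is stated as a fact, but the plan neither secures it with matched procedures nor tests it

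*Combined protocol and SAP*

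**What the plan says.** Section 10.1, Step 3b gives the basis for participant blinding. The first ground is sensory: "Since the effects from the anesthetic block will still be active". The second is visual: positioning, and a drape held by someone outside the study. From these it concludes that "participants will not know that there is nothing being injected into the area". Steps 3a and 3b add that the consent wording will not let participants work out their arm from the injection technique.

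The block is not standardised. Section 10.2 lists it as "Spinal, adductor or femoral nerve block determined by anesthesiology". Section 9.2 places the injections right after the TKA, and Steps 3a and 3b place them on POD 0.

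In the active arm the sites are "the vastus medialis, vastus lateralis, medial, and lateral gastrocnemius muscle bellies by utilizing anatomical landmarks". Step 3a specifies: "A total of eight injections will be administered with a total of 4 mLs of 1% lidocaine without epinephrine". It then adds: "The local anesthetic will be massaged into the area to ensure the medication disperses thoroughly into the muscle belly". In the sham arm, Step 3b has a needle placed in the epidermis for 3-5 seconds with nothing injected.

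The primary outcome is the participant's own 0-100 VAS at POD1, week 2 and week 6 (9.2). Section 11.1 summarises block type by arm and adjusts for it if the arms differ. It contains no assessment of blinding.

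**The concern.** The VAS is reported by the person whose blinding is in question. If participants can tell which procedure they had, an expectation effect enters the arm difference and cannot be separated from an effect of the injection. The plan treats this as settled by the block and the drape. A drape does not affect touch, and the plan does not ensure that the block removes sensation at the sites. If blinding fails, nothing collected would show it, and the information cannot be recovered later.

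**Working it through.** **1. What the plan says about feeling the injections.**

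| Section | Content |
|---|---|
| 10.1, Step 3b | Block active, so participants will not know that nothing is injected |
| 16.1 | Pain from the intervention is expected, and eases once the local anesthetic works |
| 10.2, Complications | Severe pain from the injections is a coded category |
| 13.6 | Not tolerating all the injections is a listed reason to withdraw |

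The last three entries allow that the injections will be felt in at least some patients. Step 3b assumes that they will not. The relief described in 16.1 also depends on the lidocaine, which only the active arm receives.

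**2. What differs between the arms (Step 3a against Step 3b).**

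| Feature | Active | Sham |
|---|---|---|
| Depth | Muscle, 1½-inch needle | Epidermis |
| Volume | 8 × 0.5 mL = 4 mL | None |
| Insertions per muscle | 2 | Not stated |
| Massage | Yes | Not described |
| Drape, swab, bandage | Yes | Yes |

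The visible parts are matched. The parts that can be felt are not. Section 9.2 also puts the sham needle in the dermis where Step 3b says epidermis, so these passages must be reconciled.

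**3. Whether anything checks blinding.** The procedures (10.1), data list (10.2) and analysis plan (11.1) contain no test of sensation before injection and no treatment-guess question. Comparing block type between arms tests balance, not blinding. The neurovascular evaluation in Section 16.1 is for adverse events.

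**4. What bias could do (illustration).** Inputs from 11.5 are SD 25 and two-sided alpha 0.05. Group sizes are 10, 15 and the maximum of 50 (11.2, 11.5).

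The plan's own figures reproduce. With a noncentral t and the rank-test efficiency 3/π, 15 per group at d = 1.1 gives power 0.810 (0.795 by simulation). Ten per group at d = 1.4 gives 0.822 (0.804 by simulation). The sample-size arithmetic is not in dispute.

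Now suppose there is no true effect and unblinding produces a between-arm reporting bias of b units. The chance of significance in a two-sided t test comes from a noncentral t with df = 2n − 2 and noncentrality (b/25) × √(n/2). For b = 10 and n = 15, noncentrality is 0.4 × √7.5 = 1.10, giving 0.185. For b = 10 and n = 50, it is 0.4 × √25 = 2.0, giving 0.508.

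| Assumed bias b | 10 per group | 15 per group | 50 per group |
|---|---|---|---|
| 5 | 0.071 | 0.083 | 0.168 |
| 10 | 0.135 | 0.185 | 0.508 |
| 15 | 0.246 | 0.355 | 0.844 |
| 20 | 0.395 | 0.562 | 0.977 |

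The nominal rate is 0.05. The values of b are assumptions; the documents give none. Under any fixed bias, recruiting more patients raises the false-positive rate.

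**5. What a guess question could detect.** Take a per-arm index equal to the share guessing correctly minus the share guessing wrongly, from −1 to 1. If everyone guesses and half are right, the 95% half-width is 1.96 × 2 × √(0.25/n): 0.62 at n = 10, 0.51 at n = 15 and 0.28 at n = 50. At 15 per arm, an index near 0.5 means about 75% correct against 25% wrong. Only gross unblinding would show.

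**The case against.** The best defence has four parts. Section 9.2 places the injections right after surgery, when a block is likely to be working. Sight is well controlled and the consent wording is guarded. Each participant has one procedure only, so nobody can compare a deep injection with a superficial one, and feeling something is not the same as knowing one's arm. The pain entries in 10.2, 13.6 and 16.1 may be routine risk text.

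Much of this is fair. It would be wrong to say that timing is tied only to POD 0. What remains is that no window relative to the block is set and Steps 3a and 3b do not repeat the 9.2 timing. Having had only one procedure makes correct guessing less likely, but a cue such as massage in one arm needs no comparison to be informative. If 16.1 is generic text, it still contradicts Step 3b.

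A reader might go further and infer that an adductor or femoral block leaves the calf sensate, so that the gastrocnemius injections, 4 of the 8, must be felt. The documents do not support this. They give no block territories and do not say whether blocks are combined. It is an assumption for anesthesiology to confirm, and the point does not depend on it. Nor do the documents show that blinding will fail, or in what share of patients.

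**Conclusion.** The concern holds as a gap between claim and evidence. Participant blinding of the primary outcome is stated as a fact. It rests on an unstandardised block with no sensory check, it conflicts with the plan's own expectation of injection pain, and the procedures differ in ways that can be felt. Nothing measures whether it held.

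The size of any bias cannot be derived from the documents. The false-positive rates in the working rest on an assumed bias, SD 25 and no true effect. They show that a modest bias would matter, not that one exists. Multiplying an assumed share unblinded by an assumed per-person shift gives a figure in VAS units, but it would carry no more evidence than its two inputs.

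This should be corrected. It does not invalidate the design, but it limits how firmly a VAS difference can be attributed to the injection.

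**What to change.** 1. Reconcile Steps 3a and 3b with 16.1 (and the sham depth in 9.2). Describe the sham so that its number of insertions and its handling of the site, including massage, match the active arm. This removes a cue that would otherwise only be measured.
2. Record injection time, block type (already collected) and whether touch is felt at each of the four sites before injection.
3. Ask participants whether they think they had the real injection, the sham, or do not know. Ask soon after the injections and before the POD1 VAS. Asked after the VAS, the answer is confounded with pain relief.
4. In 11.1, report guesses by arm with a confidence interval, and descriptively by block type. State that at 15 per arm the half-width is about 0.5. Any analysis restricted to participants with no sensation at any site should be omitted or labelled exploratory, because arms of 10-15 are too small to split.
5. Describe participant blinding as intended, not assured, and qualify the VAS conclusion if guesses differ from chance. A result compatible with chance at this size should not be read as proof that blinding held.

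The cost is four tick boxes, a time, one question and a short table. The downside is that the question may itself prompt guessing.

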The aim is of this study is to explore the effect of a pain intervention (ie, trigger point injection) vs. a sham injection on managing post-surgical pain and reducing the reliance on systemic opioid analgesics. Outcomes include the VAS on POD1 and week 2 and week 6 follow-up appointments. Opioid use will also be evaluated during these intervals.

9.4 Study Design:

Describe study design in one to two sentences (e.g., prospective, use of existing records/data /specimens, observational, cross-sectional, interventional, randomized, placebo-controlled, cohort, etc.). Specify the phase – Phase I, II, III, or IV – for FDA-regulated investigational drug research

Prospective, interventional study comparing trigger point injections vs. sham injections on VAS pain scale ratings and opioid use.

9.5 Target Population:

Describe the population to whom the study findings will be generalized

DoD beneficiaries aged 45 years and older who will be receiving a TKA, on either knee.

9.6 Benefit to the DoD:

State how this study will impact or be of benefit to the Department of Defense

The purpose of this study is to explore a unique pain management modality to reduce the use of opioids following a routine surgery in the military hospital setting. This will benefit the Department of Defense by improving post surgical pain, decreasing overall opioid use which in turn may lead to decrease rate of opioid use disorders, shorter inpatient stays and decrease adverse medication side effects.

10.0

Study Procedures, Data Management, and Privacy

10.1 Study Procedures:

Describe step-by-step how the study will be conducted from beginning to end

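### The named opioid sources do not match the MME intervals around discharge: staff-given doses after the POD1 visit have no source, and home doses before it land in the wrong interval (minor, secondary outcome only).

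*Combined protocol and SAP*

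**What the plan says.** Section 9.2 defines the secondary outcome as "how much opioid medication (ie, MME) was used in the immediate post-operative period through the week 6 follow-up visit". Section 10.2 divides it into three adjoining intervals: POD0 to POD1, POD1 to week 2, and week 2 to week 6. It names a calculator but no source.

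The sources are in section 10.1:

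- Step 4, on POD0, obtains "morphine milligrams equivalents (MME) using the Medication Administration Record (MAR) Summary".
- Step 5, on POD1, has the investigator "review the MAR Summary to obtain and calculate the total MME from POD0 to POD1 using MDCalc". The Opioid Use questionnaire, given at POD1, week 2 and week 6, "will be used to document average opioid use following discharge". Participants are asked to bring their opioids to the week 2 and week 6 visits for counting.
- Step 7 calculates MME at weeks 2 and 6 once that supply has been accounted for.

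Section 11.1 compares MME between the injection groups at each time point. No section states when patients are discharged.

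**The concern.** The plan changes source at the POD1 visit, but a patient's opioid supply changes at discharge, from staff-given to self-administered. Unless the two moments coincide, some doses belong to one interval while the named source for that interval does not record them.

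Because MME is compared by arm interval by interval, a dose that is lost or put in the wrong interval alters a planned comparison. Reducing reliance on opioids is part of the stated aim (section 9.3), so the MME totals should be computable in one way only from the protocol text.

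**Working it through.** **The plan's own figure.** There is none for MME. The only calculation is for VAS in section 11.5. It reproduces: with a noncentral t and the sample size scaled by 3/π for the Wilcoxon test, power is 0.810 at 15 per group with effect size 1.1, and 0.822 at 10 per group with 1.4. It does not depend on the opioid record.

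**Sources set against intervals.** Inputs are the outcome (9.2), the intervals (10.2) and the sources (10.1 Steps 4, 5 and 7).

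| Patient | Doses | Interval they belong to | Named source |
|---|---|---|---|
| Discharged after POD1 visit | End of surgery to POD1 visit | POD0–POD1 | Medication record |
| | POD1 visit to discharge, given by staff | POD1–week 2 | None |
| | Discharge to week 2 | POD1–week 2 | Count, questionnaire |
| Discharged before POD1 visit | End of surgery to discharge | POD0–POD1 | Medication record |
| | Discharge to POD1 visit, at home | POD0–POD1 | Not in the record. The POD1 questionnaire asks, but no rule adds the answer to this total |
| | POD1 visit to week 2 | POD1–week 2 | Count, questionnaire |

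The week 2 to week 6 interval does not have this problem if discharge is before week 2.

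**Effect on one patient.** Let u be staff-given MME between the POD1 visit and discharge, and h be home MME before the POD1 visit. Assume that the count yields use as supply dispensed minus supply remaining. No count is planned at POD1, so the week 2 count cannot separate h from later use.

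- Discharged after the visit: interval 1 is right; interval 2 = true − u; the total through week 6 = true − u.
- Discharged before the visit: interval 1 = true − h; interval 2 = true + h; the total is right, but both interval values are wrong.

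**Effect on the comparison.** Let U and H be the arm means of u and h over all patients in the arm (zero where not applicable). The error in the measured sham-minus-treated difference is:

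- Interval 1: −(H_sham − H_treated)
- Interval 2: −(U_sham − U_treated) + (H_sham − H_treated)

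The documents give none of these quantities. To show only how the U term behaves, write U = (share still in hospital) × (mean uncounted MME per such patient). Every input below is an assumption, at 15 per arm.

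| Still in hospital, sham vs treated | Uncounted MME each | U_sham vs U_treated | Error in difference |
|---|---|---|---|
| 5/15 vs 2/15 | 20 | 6.7 vs 2.7 | −4.0 |
| 5/15 vs 2/15 | 40 | 13.3 vs 5.3 | −8.0 |
| 5/15 vs 2/15 | 60 | 20.0 vs 8.0 | −12.0 |
| 5/15 vs 5/15 | 40 vs 30 | 13.3 vs 10.0 | −3.3 |
| 5/15 vs 5/15 | 40 | 13.3 vs 13.3 | 0 |
| 2/15 vs 5/15 | 40 | 5.3 vs 13.3 | +8.0 |

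The sign follows the assumption. Without an MME SD, none of these values can be called large or small.

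**The case against.** The strongest reply is that discharge may come at about POD1. The POD1 contact is called a visit, it uses the orthopedic technician's intake form, all participants then receive a questionnaire on use after discharge, and Step 4 lists discharge disposition among the POD0 items. If everyone has gone home by then, the staff-dose gap is empty. This stands as a reason to expect few affected patients. It does not remove the problem: early discharge replaces the missing doses with misplaced ones. The POD1 questionnaire is a named source for those home doses, so what is lacking there is an assignment rule. One can also say that 10.2 calls for a total and does not forbid using the medication record later. That is true, but the steps as written do not call for it.

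Three stronger readings are tempting, and the documents do not support them.

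- **Pre-operative and intra-operative doses contaminate the first total.** A reader might infer this because Step 3a equates POD 0 with the day of the operation and no clock start is written. But 9.2 frames the outcome as post-operative, section 20.2 expands POD as post-operative day, and Step 4 places the review after surgery. Whether the MAR Summary holds intra-operative doses is not stated. One clarifying phrase is enough.
- **Doses given after surgery but before the injection should be excluded.** They cannot respond to treatment, but they belong to the outcome as 9.2 defines it. The injection is planned "immediately following TKA to assess the effect on pain scores", and Step 3b relies on a block that is still working: "Since the effects from the anesthetic block will still be active". The plan thus points to a short interval, although it does not state its length.
- **The bias runs against the intervention and hides an opioid-sparing effect.** This needs shorter stays or lower in-hospital use in the treated arm. On stays, the text offers only the hope in 9.6 that lower opioid use, "which in turn may lead to decrease rate of opioid use disorders, shorter inpatient stays", might follow.

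**Conclusion.** The mismatch holds on the text. If the steps are followed as written, POD1-to-week-2 MME is understated for any patient given opioids by staff after the POD1 visit. For any patient who takes opioids at home before that visit, MME moves from the first interval to the second. The second statement assumes that the count measures supply dispensed minus supply remaining.

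The size and direction of any bias between arms cannot be determined from the documents. It is zero if the uncounted and misplaced MME have equal means in the two arms. The number of patients affected may be small.

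This is a minor point. It concerns a secondary outcome for which no sample size was calculated, and it leaves the primary VAS outcome and its sample size unchanged. It is still worth correcting before data collection, because the change is cheap and makes the interval totals reproducible.

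**What to change.** In sections 10.1 and 10.2:

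1. Extend the medication record review through actual discharge, and assign each recorded dose to its interval by its recorded time.
2. State that the POD0–POD1 total starts at end of surgery, consistent with 9.2.
3. For patients home before the POD1 visit, add the use they report on the questionnaire up to that visit to the first interval, and subtract the same amount from the use derived from the week 2 count. The form must yield an amount taken since discharge for this; an average alone would need a conversion rule.

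The cost is protocol wording and a slightly longer review of a record that the investigator already opens. The small home-use portion is self-reported and so less exact than a count. No visits are added.

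### If anyone goes home before the POD1 visit, POD0-POD1 MME omits their home doses, because the hospital record is the only source named for that interval

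*Combined protocol and SAP*

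**What the plan says.** MME is the secondary outcome, covering the immediate post-operative period up to week 6 (Section 9.2), and is compared between arms at each time point (Section 11.1).

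- **Source for the first interval.** Section 10.1 Step 4, the POD0 chart review, obtains "morphine milligrams equivalents (MME) using the Medication Administration Record (MAR) Summary". Step 5, at POD1, has the investigator "review the MAR Summary to obtain and calculate the total MME from POD0 to POD1".
- **Intervals.** Section 10.2 says of MME: "Will be measured from POD 0 to POD1, then a total MME will be calculated from POD1 to week 2", followed by week 2 to week 6. It adds no further source for the first interval.
- **Questionnaire.** Step 5 says: "The Opioid Use questionnaire will be used to document average opioid use following discharge". It continues: "Both questionnaires will be completed by all participants at POD1, week 2 and week 6 visits".
- **Tablet counts.** Before the POD1 visit ends, participants are asked to "bring in their opioids to be physically counted at their week 2 and week 6 visits". No count is made at POD1, and no starting quantity is given for the week 2 count.
- **Discharge.** Section 10.2 collects destination only (skilled nursing facility or home), read from the discharge summary. No discharge date or time is listed, and no section requires a stay until POD1.

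**The concern.** An inpatient administration record cannot contain doses that a patient takes at home. If a participant leaves before the POD1 visit, the stated rule produces a POD0-POD1 total that stops at discharge. The one instrument given at POD1 that asks about use after discharge is not linked to that total, and as described it records an average, not an amount.

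POD0-POD1 is the interval closest to a single lidocaine injection given on POD0. If discharge timing differed between arms, its MME would partly measure hours in hospital. The planned analysis could not detect this: the group comparisons in Section 11.1 include discharge destination, but timing is not collected. Any unwritten handling of home doses would also be decided by investigators who can know the arm, since the subject ID carries an E or S suffix (Section 10.1 Step 2).

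**Working it through.** **No plan figure to reproduce.** The protocol states no mean, standard deviation, effect or power for MME; its sample size rests on VAS alone. The check is therefore a reading of sources followed by an illustration.

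**Step 1: where does a home dose before POD1 go?**

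| Possible place | Would it capture the dose? |
|---|---|
| Hospital record, POD0-POD1 | No; the record ends at discharge |
| POD1 questionnaire | Possibly asked, but not used in MME |
| POD1 tablet count | None is made |
| Week 2 tablet count | Only if counted against the dispensed quantity, and then booked to POD1-week 2 |

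The dose is either lost or placed in the wrong interval. In both cases POD0-POD1 MME is too low.

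**Step 2: size under equal true use.** Let pT and pS be the shares home before POD1 in the trigger point and sham arms, and h the mean MME taken at home before the POD1 visit. With the same true use in both arms:

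recorded difference (trigger point minus sham) = −(pT − pS) × h

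**Step 3: illustration.** All inputs are assumed: 2 MME per hour for 24 hours gives a true total of 48. Discharge at 8 hours leaves 16 on the record and h = 32. For a share q discharged at 8 hours:

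recorded mean = (1 − q) × 48 + q × 16

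| Home at 8 hours, trigger point v sham | Recorded means | Difference | As share of recorded sham total |
|---|---|---|---|
| 50% v 30% | 32.0 v 38.4 | −6.4 | 6.4 / 38.4 = 16.7% |
| 40% v 20% | 35.2 v 41.6 | −6.4 | 6.4 / 41.6 = 15.4% |
| 30% v 30% | 38.4 v 38.4 | 0 | 0; both totals 20% below 48 |

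The first two rows share a 20-point gap, so they give the same difference: 0.20 × 32 = 6.4.

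**Step 4: range over other assumed inputs.**

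| Shares home before POD1 | h = 7.5 | h = 15 | h = 30 |
|---|---|---|---|
| 30% v 10% | −1.5 | −3 | −6 |
| 50% v 20% | −2.25 | −4.5 | −9 |
| Equal | 0 | 0 | 0 |

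**Step 5: false-positive rate.** Simulation of 10,000 trials per setting: equal true use, normal with assumed mean 40 and SD 20 MME, h subtracted for those home early, totals floored at 0, two-sided t test at 0.05. The ranges run from h = 15 to h = 30.

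| Shares home before POD1 | 15 per arm | 50 per arm |
|---|---|---|
| 20% v 20% | about 0.05 | about 0.05 |
| 30% v 10% | 0.07 to 0.11 | 0.11 to 0.23 |
| 50% v 20% | 0.09 to 0.16 | 0.19 to 0.44 |

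**Step 6: after the fix.** Adding home doses up to the POD1 visit to the record total makes the term −(pT − pS) × h equal to 0 for any discharge pattern, apart from error in self-report.

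**The case against.** The strongest reply is that the protocol never says anyone goes home before POD1. The questionnaire's reference to discharge describes one form used at three visits and fits weeks 2 and 6 well enough. Step 4 lists discharge disposition in the POD0 review, but that is a list of chart variables. It also includes complications, and surgical site infection is one of those defined in Section 10.2; it would seldom be known on POD0. A reader might infer that the plan expects same-day discharge. The text suggests it but does not establish it. If every participant stays until POD1, the omission is nil, although the post-discharge item then has nothing to record at POD1.

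A reader might also infer that the injection is expected to shorten stays, so that the active arm's MME would fall artificially. Section 9.6 does not support this. It lists "shorter inpatient stays and decrease adverse medication side effects" among things that lower opioid use may bring about, so shorter stays are a possible consequence of reduced use and not an effect expected while use is unchanged. A shorter stay also need not end before POD1. Nor can one say without qualification that early discharge will look like opioid sparing between arms: that requires timing to differ by arm.

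Finally, if the week 2 count starts from the dispensed quantity, the missing doses reappear in POD1-week 2 and the cumulative MME is preserved. These limits all stand. What remains is that the stated rule is incomplete for anyone home before POD1, and nothing in the protocol excludes such participants.

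**Conclusion.** The concern holds in conditional form. If any participant is discharged before the POD1 visit, POD0-POD1 MME is understated for that participant under the stated rule. The by-time-point arm comparison is biased if discharge timing differs by arm; with equal timing the difference is unbiased and both arm totals are too low.

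The size cannot be taken from the documents, which give no early-discharge rate, home dose or MME variability. On the assumed inputs above, a 20-point gap in early discharge gives a false difference of 6.4 MME, about 15% to 17% of the recorded sham total. At 15 per arm the effect on the false-positive rate is modest; it grows at the 50-per-arm maximum.

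The reach is limited to the interval analysis of a secondary outcome, provided the week 2 count recovers the doses. If it does not, the cumulative MME is short as well. The VAS primary outcome is unaffected.

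**What to change.** In Section 10.1 Step 5 and the MME entry of Section 10.2:

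- Define POD0-POD1 MME as doses on the hospital record plus opioids taken at home between discharge and the POD1 visit.
- Take the home doses from the POD1 Opioid Use questionnaire, worded as the number of tablets taken since discharge, with a not-applicable option for anyone still in hospital.
- Start the POD1-week 2 interval from the dispensed quantity less those tablets, so that no dose is counted twice. This avoids a POD1 count, which would need an earlier instruction because participants are first asked at that visit to bring their opioids.
- Record discharge date and time from the discharge summary already being reviewed.

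If all participants do stay until POD1, one sentence saying so settles the matter.

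The cost is small: edits to two sections, one questionnaire item (the form is not reproduced, so its present wording could not be checked), the dispensed quantity as a recorded starting value, and discharge date and time as added data. The form and the visit already exist. The downside is that a few hours of self-reported doses are added to a total otherwise taken from the record.
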